## Safety Monitoring

Post-vaccination safety surveillance will be carried out from day 1 through day 5 post-vaccination. The following data will be collected and recorded daily: (i) evening rectal temperature; (ii) local swelling and redness; (iii) generalized rash; (iv) seizures; (v) any unexpected reactions.

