**ELIGIBILITY/FOLLOW-UP STATUS**

Woman has left  
the cluster

DETERMINE WHERE THE WOMAN WENT

IF MOVED OUT OF DHAKA, SHE IS NOT ELIGIBLE TO  
CONTINUE THE STUDY

IF MOVED WITHIN DHAKA, GET INFORMATION ON WHERE  
MOVED TO AND DISCUSS FOLLOW-UP PLANS WITH FRO

Woman  
temporarily  
absent

DETERMINE WHEN WOMAN IS EXPECTED TO RETURN AND RECORD DATE ON  
FOLLOW-UP REGISTER

SECTION 0: IMMUNIZATION (DAY 0)

IM01a. Trivalent oral polio vaccine has been given to infant:

- Yes ..... 1
- No ..... 0 [GO TO QIM01c]
- Yes, through EPI ..... 2

IM01b. Date and time of oral polio vaccination; [GO TO Q IM02a]:

Date: \_\_\_/\_\_\_/\_\_\_/ Time: \_\_\_\_\_ a.m./p.m.

IM01c. Reason for not giving oral polio vaccine:

- (1): \_\_\_\_\_ CODE: \_\_\_\_\_
- (2): \_\_\_\_\_ CODE: \_\_\_\_\_
- (3): \_\_\_\_\_ CODE: \_\_\_\_\_

IM02a. DPT-HiB vaccine has been given to infant:

- Yes ..... 1
- No ..... 0 [GO TO Q IM02C]
- Yes, DPT through EPI ..... 2

IM02b. Date and time of DPT-HiB vaccination; [END OF INTERVIEW]:

Date: \_\_\_/\_\_\_/\_\_\_/ Time: \_\_\_\_\_ a.m./p.m.

IM02c. Reason for not giving DPT-HiB vaccine:

- (1): \_\_\_\_\_ CODE: \_\_\_\_\_
- (2): \_\_\_\_\_ CODE: \_\_\_\_\_
- (3): \_\_\_\_\_ CODE: \_\_\_\_\_

END OF INTERVIEW DAY 0

SECTION 1: DAY 1 OF FOLLOW-UP:

- IM11 How is your baby (body/health) now?
  - Ill ..... 1
  - Some what okay ..... 2
  - Well ..... 3
- IM12 Did your baby cry more than usual since yesterday?
  - Yes ..... 1
  - No ..... 0
  - Don't know ..... 9
- IM13 Did your baby eat usual, less than usual or more than usual since yesterday?
  - Less than usual ..... 1
  - More than usual ..... 2
  - Normal, as usual ..... 0
  - Don't know ..... 9
- IM14 Has your baby been more, less or normal active since yesterday?
  - Less than usual ..... 1
  - More than usual ..... 2
  - Normal, as usual ..... 0
  - Don't know ..... 9

[EXAMINATION OF INFANT BY STUDY NURSE]:

- IM15 Temperature (Rectal) .....     °C
- IM16 Infant has local swelling and/or redness at injection site:
  - Yes ..... 1
  - No ..... 0
- IM17 Infant has rash all over its body:
  - Yes ..... 1
  - No ..... 0
- IM18 Infant has\ has had seizure:
  - Yes ..... 1
  - No ..... 0
- IM19 Condition of infant:
  - Restless, Irritable ..... 1
  - Lethargic ..... 2
  - Well Alert ..... 0
- IM110 Other comments/observations:

END OF INTERVIEW DAY 1

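### Fever, injection-site reactions and rash that resolve before the Day 1 examination are not prompted for after any vaccine dose

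*Protocol*

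**What the plan says.** Protocol, Safety Monitoring: "Post-vaccination safety surveillance will be carried out from day 1 through day 5 post-vaccination". The items to be recorded daily are "i) evening rectal temperature; (ii) local swelling and redness; (iii) generalized rash; (iv) seizures; (v) any unexpected reactions". Only the temperature is tied to a time of day.

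Immunization Interviews form, annexed to the protocol:
- The vaccination day carries the title "SECTION 0: IMMUNIZATION (DAY 0". The section asks whether each vaccine was given, when, and if not, why. After a DPT-Hib dose the interview stops at "IM02b. Date and time of DPT-HiB vaccination; [END OF INTERVIEW", and the section closes with "END OF INTERVIEW DAY 0".
- The Day 1 sheet opens with questions to the mother. One asks how the baby is now; those on crying, eating and activity look back one day, for example "IM12 Did your baby cry more than usual since yesterday".
- A nurse's examination follows: rectal temperature (IM15), then "IM16 Infant has local swelling and/or redness at injection site" and "IM17 Infant has rash all over its body", both in the present tense. The seizure item (IM18) covers past as well as present seizures. A free-text comments field (IM110) ends the sheet.
- The face sheet numbers five visit dates but shows one field for the time of visit.

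The combined vaccine is given at 6, 10 and 14 weeks (Immunization and Serology). The Randomization section describes the trial as one of safety as well as immunogenicity.

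**The concern.** Reaction data are collected from the day after each dose, and nothing systematic is collected on the day itself. For three of the listed reactions the Day 1 sheet does not look back over the missing hours. An infant who is febrile on the evening of vaccination and afebrile at the next day's reading has no prompted field in which that fever would appear. The same goes for swelling, redness or rash that fades overnight.

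What is at stake is the meaning of the reaction rates from the protocol's only post-vaccination reaction plan. Unless labelled, a rate described as fever within five days of vaccination would be read as including the first day. Once the doses have been given, the missing observations cannot be recovered.

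**Working it through.** **No planned figure to reproduce.** The protocol states no hours, expected reaction rate or sample size for this point.

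**Step 1: which day is Day 1?** Safety Monitoring alone might be read as counting the vaccination day as Day 1. The form rules this out: Day 0 is the vaccination day, and the Day 1 questions refer back to the day before.

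**Step 2: which items cover the interval between the dose and the Day 1 examination?**

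| Item | Day 0 | Day 1 | Interval covered by a prompt? |
|---|---|---|---|
| Crying, eating, activity (IM12–IM14) | none | asked over the past day | yes |
| Seizure (IM18) | none | present or past | yes |
| Temperature (IM15) | none | reading at examination | no |
| Swelling or redness (IM16) | none | state at examination | no |
| Rash (IM17) | none | state at examination | no |
| Other comments (IM110) | none | free text | only if volunteered |

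**Step 3: how long is the interval?** Let v be the clock hour of the dose and o the clock hour of the Day 1 observation:

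gap = 24 − v + o

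The form records v for each infant, but no clinic or visit hours are planned. All hours below are assumptions.

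| Assumed dose hours | Assumed Day 1 observation | Shortest gap | Longest gap |
|---|---|---|---|
| 08:00–17:00 | evening, 18:00–20:00 | 24 − 17 + 18 = 25 h | 24 − 8 + 20 = 36 h |
| 09:00–16:00 | evening, 17:00–21:00 | 24 − 16 + 17 = 25 h | 24 − 9 + 21 = 36 h |
| 09:00–13:00 | evening, 18:00–20:00 | 24 − 13 + 18 = 29 h | 24 − 9 + 20 = 35 h |
| 08:00–17:00 | daytime, 08:00–17:00 | 24 − 17 + 8 = 15 h | 24 − 8 + 17 = 33 h |
| 09:00–13:00 | morning, 09:00–12:00 | 24 − 13 + 9 = 20 h | 24 − 9 + 12 = 27 h |

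The evening rows apply to temperature. They apply to site and rash only if one evening visit covers all items. The form lists them in one examination, which points that way, but gives no visit hour. Otherwise the daytime rows apply to those two items.

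**Step 4: effect on a rate.** Let p be the true rate of a reaction and s the share of affected infants whose reaction is over before the Day 1 examination and is not volunteered. Then:

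observed rate = p × (1 − s)

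The documents give neither p nor s, so the shortfall has a direction but no computable size.

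**Step 5: effect on a comparison of groups.** If s is the same under zinc and placebo, the ratio of rates is unchanged, since p₁(1 − s) / p₀(1 − s) = p₁ / p₀. The difference shrinks to (1 − s)(p₁ − p₀).

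**Step 6: doses exposed.** Planned enrolment gives at most 122 infants × 4 groups × 3 doses = 1,464 dose visits. This is a ceiling, because 122 already includes the 15% allowance for attrition.

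**The case against.** The strongest reply is that starting the day after vaccination is a deliberate choice, applied consistently in text and form, in a trial whose two objectives, hypothesis and sample-size outcomes are all immunological. No estimate of reaction rates and no zinc-versus-placebo comparison of reactions is planned. This stands, and it limits the weight of the point: there is no contradiction, and no stated objective fails. It does not close the gap, because the protocol calls the trial a safety trial and collects these items.

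Several stronger readings are tempting but unsupported:

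- **A reader might infer that nothing about the first day is recorded.** Seizures, crying, eating and activity are covered by look-back wording, the free-text field can hold a volunteered report, and reactions that persist to Day 1 are counted. The gap is the lack of a prompt for three transient reactions.
- **A reader might infer that the evening reading cannot be checked at all.** The face sheet has a visit-time field. The limitation is that one field serves five dates.
- **A reader might infer that these would be the first reaction data for this vaccine from a developing country.** The statement under Significance concerns immune responses, and the similar sentence under Sample Size stands among assumptions on serological response. Neither is about reactions.
- **A reader might infer a bias between zinc and placebo.** All groups follow one schedule, and nothing in the documents suggests that s differs by group.

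**Conclusion.** The point holds as a limited weakness in data capture. After each of the three doses, a fever, site reaction or rash that resolves before the Day 1 examination is not systematically recorded, so rates of these reactions are understated.

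The unobserved interval is about 25 to 36 hours for temperature, and about 15 to 33 hours for site and rash if these are checked earlier in the day. Both ranges rest on assumed clinic and visit hours and should not be quoted as figures from the protocol. The size of the understatement cannot be derived from the documents. The loss does not by itself favour either supplement group.

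This is a worthwhile, low-cost improvement. It does not touch the immunological outcomes or the sample size.

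**What to change.** 1. Add three prompted questions to the mother on the Day 1 sheet, each covering the time since vaccination: fever, swelling or redness at the injection site, and rash. No seizure item is needed, because IM18 already looks back.
2. Add a clock time beside each daily temperature. With the vaccination time already on the Day 0 section, this gives the actual gap for every infant and shows whether readings were taken in the evening.
3. Report the measured temperature outcome as starting the day after vaccination, and report recalled fever separately.

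The cost is a few form items and a few minutes at visits already planned. Recalled fever is less accurate than measured fever, which is why the two should not be pooled.

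Two larger changes are not recommended. Moving the five readings to begin on the vaccination evening would give up Day 5, which the protocol specifies, and the documents do not show that to be a better trade. Adding a visit on the vaccination evening would require up to 1,464 extra visits.

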## Sample Size:

The sample size (Table 3) was calculated to detect differences between treatment groups with 80% power and a type 1 error of 5% (i.e. 95% significance). In previous immunogenicity trials in the UK. With DTP-Hib vaccine the sero-response to PRP was 82% (22). There are no prior data available using H.Influenza type B vaccines in developing countries. We have assumed that approximately 30% of Bangladeshi infants (20% less than the general U.S. population) will have an antibody level of  $\geq 0.15 \mu\text{g/ml}$  to PRP if they are given three doses of the vaccine. We have also assumed that with zinc supplementation, their immune responses will be the same as the U.S. infants.

Similarly, after three doses of TOPV 73% of children in developing countries have detectable antibody level to poliovirus type, thus we have assumed that with zinc supplementation, their immune responses will be the same as industrialized countries, where rates of conversion following the administration of three doses of TOPV approaches 100%.

In developing countries, the percentage of anergic children to tuberculin testing approaches 70%. We assume that with zinc supplementation the cellular immune response will improve and anergic children will decrease from 70% to 50%.

In order to allow 15% for attrition, we anticipate recruiting approximately 122 infants per group during the study period.

Table 3

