## ASSUMPTIONS FOR SAMPLE SIZE CALCULATIONS

Outcome Variable	Control Group	Expected Outcome	No. required in each cell*	No. to be enrolled in each group†
% with antibody level above 0.15 µg/ml to PRP	30%	98%	103	113
% with detectable antibody to poliovirus type 1	70%	95%	38	44
% anergic for tuberculin testing	70%	50%	103	119

\* 80% power (Type 2 error of 20%) and Type 1 error of 5%

† Assuming that 15% will not complete the follow up

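### The Hib row of Table 3 is inconsistent: 30% versus 98% needs about 10 infants per group, and the printed 103 belongs to the 30% versus 50% that the text implies

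*Protocol*

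**What the plan says.** The Sample Size section of the protocol sets the calculation "with 80% power and a type 1 error of 5% (i.e. 95% significance". It does not say whether the test is two-sided or which formula was used.

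- **Hib, text.** The only observed response cited is 82%, from the UK. The control assumption is "We have assumed that approximately 30% of Bangladeshi infants (20% less than the general U.S. population". For the zinc group: "We have also assumed that with zinc supplementation, their immune responses will be the same as the U.S. infants". No U.S. rate is stated.
- **Hib, Table 3.** The row reads "with antibody level above 0.15 µg/ml to PRP 30% 98% 103 113": control 30%, expected 98%, 103 required per cell, 113 to be enrolled.
- **Polio, text.** The control assumption is that "after three doses of TOPV 73% of children in developing countries have detectable antibody level to poliovirus", with zinc infants assumed to reach the near-100% conversion of industrialized countries.
- **Polio, Table 3.** The row "with detectable antibody to poliovirus type 1" prints 70% versus 95%, 38 required, 44 to be enrolled.
- **Tuberculin, text and Table 3.** 70% versus 50% anergic in both; the table gives 103 required and 119 to be enrolled.

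The table's footnotes repeat "80% power (Type 2 error of 20%) and Type 1 error of 5"% and give 15% non-completion. The text plans to recruit about 122 infants per group.

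**The concern.** Two things in the Hib row do not fit. The printed rates are 68 points apart, yet the required number equals that of the tuberculin row, where the rates are 20 points apart. And the text describes a 20% shortfall made good by zinc, which on a percentage-point reading ends at 50%, not 98%. The plan therefore carries 50% (by implication), 82% (UK) and 98% (table) as competing reference responses.

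Hib is the first-named vaccine in both objectives and in the hypothesis. At stake is which Hib effect the trial can say it was sized to detect, and from what control rate.

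**Working it through.** **Inputs.** Rates, required numbers, enrolment, 80% power, 5% type 1 error and 15% attrition are from the Sample Size section and Table 3. Two-sided testing and equal allocation are my assumptions.

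**Formula.** With d = |p1 − p2| and p̄ = (p1 + p2)/2:

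- Uncorrected: n = [1.96·√(2p̄(1−p̄)) + 0.842·√(p1(1−p1) + p2(1−p2))]² / d²
- Continuity-corrected: n′ = (n/4)·[1 + √(1 + 4/(n·d))]²

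**Step 1: reproduce the tuberculin row.** For 70% versus 50%, p̄ = 0.60 and n = (1.3579 + 0.5708)²/0.04 = 93.0, so n′ = 102.8, rounded up to 103. The plan's figure is reproduced, with continuity correction.

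**Step 2: the Hib row as printed.** For 30% versus 98%, p̄ = 0.64 and n = (1.3305 + 0.4033)²/0.4624 = 6.5, so n′ = 9.2. That is 7 uncorrected and 10 corrected. Fisher's exact test has 76.5% power at 8 per group and 86.6% at 9. Across one- and two-sided tests, pooled, unpooled and arcsine formulas, and 80% or 90% power, the answers lie between 4 and 11. None approaches 103.

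**Step 3: the effect in the text.** Reading the 20% as points, the U.S. rate is 30 + 20 = 50%. 30% versus 50% is the mirror image of 70% versus 50%, so n = 93.0 and n′ = 102.8, rounded up to 103. The printed number is reproduced exactly.

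**Step 4: other readings** (per group, and uncorrected power with 103 evaluable).

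| Reading | n uncorrected | n corrected | Power at 103 |
|---|---|---|---|
| 30% vs 98% (table) | 7 | 10 | about 100% |
| 30% vs 50% (text, points) | 93 | 103 | 83.9% |
| 78% vs 98% (98% as U.S. rate, 20 points lower) | 41 | 50 | 99.5% |
| 82% vs 98% (UK rate as control) | 54 | 66 | 97.4% |
| 30% vs 37.5% (20% taken as relative, 30/0.8) | 623 | 650 | 20.5% |

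None of the readings that keep 98% gives 103.

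**Step 5: enrolment.** The other two rows multiply by 1.15: 38 × 1.15 = 43.7, so 44; 103 × 1.15 = 118.5, so 119. Dividing by 0.85 gives 103/0.85 = 121.2, so 122, which matches the recruitment target in the text. The Hib row's 113 matches neither. It allows for 1 − 103/113 = 8.8% loss, and after 15% loss it leaves 113 × 0.85 = 96.

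**Step 6: the polio row.** For the printed 70% versus 95%, n = 35.1 and n′ = 42.7, that is 36 or 43, not 38. For the text's 73% versus a full 100%, n = 23.9 and n′ = 30.9, that is 24 or 31. The Background section gives 73% for poliovirus type 1 and 70% for type 3, so the table's type 1 row carries the type 3 figure.

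**The case against.** The strongest reply is that the required number is sound and only one cell is wrong. It has force: 103 is the correct corrected figure for the text's 30% versus 50%, so replacing 98% by 50% would reconcile the rates with the required number. A reader might infer from the tenfold gap that the Hib power claim has no valid basis. The documents do not support that, because the text supplies an effect from which 103 follows.

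A second reply is that nothing in the design depends on this row. That also stands. The tuberculin row needs 103 on its own, and 122 recruited leaves 122 × 0.85 = 103.7 after attrition. A reader might infer that the trial is underpowered for Hib, for example if controls already respond at 90%, but no such control rate appears in the documents. At 103 evaluable, power exceeds 80% under the table's rates and under the text's 20-point reading.

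A third reply is text-extraction damage. It does not remove the problem. The 30% appears in both the text and the table, and if it were a misread 80%, 80% versus 98% would need 47 uncorrected or 57 corrected, still not 103. It would, however, shrink the tenfold gap to about twofold.

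On polio, it would be tempting to conclude that 38 came from a different formula than the other rows. That does not follow. The text's 73% against 98% gives 37.5 with the corrected formula, hence 38. The 98% is an assumption, as the text says only that conversion approaches 100%, but it shows that the fault may lie in the printed rates and not in the number.

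**Conclusion.** Wrong as written. The Hib row pairs a required number that fits 30% versus 50% with a printed expected rate of 98%, for which about 10 per group (7 uncorrected) would suffice. Its enrolment of 113 follows from neither 119 nor 122. The polio row's printed rates disagree with the text and give 36 or 43, not 38.

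This rests on two-sided 5%, 80% power and equal allocation. Identifying 103 with the text's effect also requires reading the 20% as percentage points, which the protocol does not say; as a relative reduction it would imply 30% versus 37.5% and 650 per group.

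The consequence is limited to which Hib effect the trial can claim to be powered for. Neither the trial's size nor the tuberculin calculation is in question.

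**What to change.** 1. State the U.S. Hib reference rate and its source, and say whether the 20% is in points or relative.
2. Make control rate, expected rate, required number and enrolment agree in the Hib row and with the text. Two consistent versions are: 30% versus 50%, 103 required, 119 to 122 enrolled according to the attrition convention; or, if 98% is the U.S. rate, a control rate of 98 − 20 = 78%, 50 required, with the power available at 103 (99.5%, uncorrected) stated beside it. The 78% is derived here and appears nowhere in the protocol, so the investigators must confirm it or give their own figure.
3. In the polio row, print the rates actually used, in line with the text and the serotype named, and recompute the number with the same formula as the other rows.
4. Name the formula (two-sided, continuity-corrected) and apply one attrition convention throughout; the table's × 1.15 gives 119, while the text's 122 fits division by 0.85.

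The cost is a few sentences in the Sample Size section and two table rows. No extra infants are needed.

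### The enrolment column of Table 3 does not follow from its own 15% loss allowance and disagrees with the correct target of 122 per group in the text

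*Protocol*

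**What the plan says.** The Sample Size section states the loss allowance and the recruitment figure together: "In order to allow 15% for attrition, we anticipate recruiting approximately 122 infants per group during the study period".

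Table 3 gives, for each outcome, the control rate, the expected rate, the number required per cell and the number to enrol per group. Its three rows read:

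- Hib: "with antibody level above 0.15 µg/ml to PRP 30% 98% 103 113"
- Polio: "with detectable antibody to poliovirus type 1 70% 95% 38 44"
- Tuberculin: "anergic for tuberculin testing 70% 50% 103 119"

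One footnote covers the required numbers, "80% power (Type 2 error of 20%) and Type 1 error of 5"%, and one covers the whole enrolment column: "Assuming that 15% will not complete the follow up".

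**The concern.** Two rows of Table 3 start from the same required number, 103, under the same 15% loss, and reach different enrolment numbers. Neither agrees with the 122 in the text. The text refers to Table 3 as the place where the sample size is set out, no row of the table shows 122, and nothing says which figure governs.

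The stake is the number of infants who reach the 24-week blood sample and skin test. The stated 80% power rests on 103 completers per group for tuberculin. Recruitment to a figure below 103/0.85 is expected to deliver fewer.

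**Working it through.** **Inputs.** Required number 103 (Hib and tuberculin) and 38 (polio), from Table 3. Loss 15%, from the Table 3 footnote and the Sample Size text. Tuberculin rates 70% and 50% anergic, from both places. Power 80% and type 1 error 5%, from the Table 3 footnote. Two-sided testing and equal allocation are assumed, since neither is stated.

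**Step 1: reproduce the required number for tuberculin.** With z = 1.960 and 0.842, the usual two-proportion formula gives

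n = [1.960 × √(2 × 0.6 × 0.4) + 0.842 × √(0.7 × 0.3 + 0.5 × 0.5)]² / 0.2² = 93.0.

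The continuity correction, n/4 × [1 + √(1 + 4/(n × 0.2))]², raises this to 102.8, so 103. The protocol's 103 is therefore the two-sided, continuity-corrected figure.

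**Step 2: inflate for loss.** To end with n completers when a share d is lost, enrol n/(1 − d).

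| Row | Required | n/0.85 | n × 1.15 | Printed in Table 3 |
|---|---|---|---|---|
| Hib | 103 | 121.2, so 122 | 118.5, so 119 | 113 |
| Polio | 38 | 44.7, so 45 | 43.7, so 44 | 44 |
| Tuberculin | 103 | 121.2, so 122 | 118.5, so 119 | 119 |

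The text's 122 is the correct inflation of 103. The polio and tuberculin rows match multiplication by 1.15. The Hib row matches neither column.

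**Step 3: expected completers at 15% loss.**

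- 113 × 0.85 = 96.1, about 7 short of 103
- 119 × 0.85 = 101.2, about 2 short
- 122 × 0.85 = 103.7, enough

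Put the other way, 113 covers a loss of 1 − 103/113 = 8.8%, and 119 covers 1 − 103/119 = 13.4%.

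**Step 4: power for 70% against 50%, two-sided 5%.**

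| Completers per group | Fisher exact | Continuity-corrected formula | Uncorrected formula |
|---|---|---|---|
| 96 (from 113) | 76.7% | 76.9% | 81.2% |
| 101 (from 119) | 79.9% | 79.2% | 83.2% |
| 103 (from 122) | 81.1% | 80.1% | 83.9% |

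**Step 5: check the Hib row's starting number.** For the printed 30% against 98%, the Step 1 formulas give 7 per cell, or 10 with the continuity correction. For 30% against 50% they give 93, or 103 with the correction. So the Hib row's 103 does not follow from the rates printed beside it.

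**The case against.** The strongest defence is that the operative number is already correct. The only sentence that says how many infants will be recruited gives 122, and recruiting 122 leaves no shortfall. That stands, and it is why the point is minor.

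Three stronger readings are tempting, and the protocol does not support them.

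- **The trial will be underpowered at 76.7%.** A reader might infer this from the 113. But every infant gives blood and has the skin test, so the same infants serve all three outcomes, and someone working from the table alone would take its largest row, 119. The 76.7% combines the tuberculin rates with the Hib row's enrolment number, and arises only if a group actually stopped at 113. No stopping rule at 113 is stated. For the Hib row's printed 30% against 98%, 96 completers give power of practically 100%.
- **Up to 36 infants will be missing.** That is 4 × (122 − 113), and it needs all four groups to stop at 113 although 119 and 122 are both stated. Groups A and B also come from a maternal cohort whose enrolment had already closed at 559 women, according to the annexed progress summary.
- **The Hib row used a 10% loss rate.** 103 × 1.10 is 113.3, but no 10% rate appears anywhere in the protocol. The 113 also differs by one digit from the 119 that the other rows' method would give, so a typing or reading error is at least as plausible. The text cannot settle it.

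What remains is that the column contradicts its own footnote and the text, whichever figure the field team would have used.

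**Conclusion.** The enrolment column of Table 3 is wrong as printed, and the 122 in the text is right. The 119 is about 2 completers short, a trivial loss: 79.9% power by Fisher's exact test against the planned 80%. The polio row is one infant short and does not drive the trial's size. The 113 is the clear discrepancy, about 7 completers short of 103, and its origin cannot be determined.

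Severity is minor, because recruitment to the figure in the text meets the requirement. The power figures assume two-sided testing at 5%, equal groups, exactly 15% loss, and 70% against 50% anergic. With an uncorrected test, power stays above 80% even at 96 completers, although the protocol's own 103 rests on the corrected calculation.

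The Hib part depends on 103 being kept for that row, and its mismatch with 30% against 98% is a separate inconsistency.

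**What to change.** Compute the last column of Table 3 as n/(1 − 0.15) throughout. The tuberculin row then reads 122, the polio row reads 45 for its stated 38, and the Hib row reads 122 if its 103 is kept. State in both the text and the table that 122 per group is the single governing target, set by the largest requirement.

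Reconcile the Hib row's 103 with its printed 30% and 98% separately. If that changes the 103, recompute the row's enrolment number by the same formula. The tuberculin row still supports 122 for the groups as a whole.

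The cost is three numbers in one table and one clarifying sentence. The recruitment figure in the text and the study procedures do not change.
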